**LIST OF ABBREVIATIONS AND RELEVANT DEFINITIONS**

ABR	General Assessment and Registration form (ABR form), the application form that is required for submission to the accredited Ethics Committee; in Dutch: Algemeen Beoordelings- en Registratieformulier (ABR-formulier)
AE	Adverse Event
CA	Competent Authority
CCMO	Central Committee on Research Involving Human Subjects; in Dutch: Centrale Commissie Mensgebonden Onderzoek
CV	Curriculum Vitae
DSMB	Data Safety Monitoring Board
EU	European Union
GCP	Good Clinical Practice
GDPR	General Data Protection Regulation; in Dutch: Algemene Verordening Gegevensbescherming (AVG)
IB	Investigator's Brochure
IC	Informed Consent
METC	Medical research ethics committee (MREC); in Dutch: medisch-ethische toetsingscommissie (METC)
(S)AE	(Serious) Adverse Event
Sponsor	The sponsor is the party that commissions the organisation or performance of the research, for example a pharmaceutical company, academic hospital, scientific organisation or investigator.
UAVG	Dutch Act on Implementation of the General Data Protection Regulation; in Dutch: Uitvoeringswet AVG
WMO	Medical Research Involving Human Subjects Act; in Dutch: Wet Medisch-wetenschappelijk Onderzoek met Mensen

## SUMMARY

**Rationale:** In the perioperative period anxiety for anesthesia and the surgical procedure is common. Breast cancer surgery patients have a higher level of anxiety compared to other patients undergoing (cancer) surgery. Relaxing breathing techniques, such as deep belly breathing are easy to learn and can have a beneficial effect on postoperative recovery. The quality of evidence in the perioperative setting is low. Slow-paced breathing at a frequency around 6 breaths per minute stimulates vagal activity and can possibly decrease anxiety, reduce mean blood pressure, postoperative pain and postoperative nausea and vomiting (PONV).

**Objective:** We aim to examine the effects of a guided slow-paced breathing technique (Slow PACE breathing) performed at induction of anesthesia in patients undergoing surgery for breast cancer on anxiety, compared to usual care. We further aim to explore effects on pre-operative blood pressure, per-operative need of hypnotics, postoperative pain and opioid use, PONV and patient satisfaction.

**Study design:** Single center, two-group, prospective, randomized controlled trial.

**Study population:** Patients scheduled for breast cancer surgery in the Antoni van Leeuwenhoekziekenhuis.

**Intervention:** Performance of pre-trained guided Slow PACE breathing by the patient at induction of anesthesia for breast surgery.

**Main study parameters:** Anxiety scored by Spielberger's State Anxiety Inventory (STAI-S).

**Nature and extent of the burden and risks associated with participation, benefit and**

**group relatedness:** There are no physical risks related to the intervention. Participants randomized in the intervention group are trained in Slow PACE breathing and will follow this short daily routine until the day of surgery. All participants are asked to complete two questionnaires at baseline, and one short questionnaire on the day of surgery and at day 1.

## 1. INTRODUCTION AND RATIONALE

### 1.1 Perioperative anxiety in breast cancer surgery patients

In the perioperative period anxiety for anesthesia and the surgical procedure is common. In a survey of ~16.000 patients in the U.K. fear for anesthesia was the most important source of perioperative anxiety. Breast cancer surgery patients have a higher level of anxiety compared to other patients undergoing (cancer) surgery, such as surgery for urological cancer.

Perioperative anxiety has a strong influence on different aspects of anesthetic care. It has a negative influence on the induction and maintenance of anesthesia, postoperative pain, and postoperative nausea and vomiting (PONV).

### 1.2 Rationale

Relaxation techniques can have a beneficial effect on anxiety, postoperative pain and possibly length of hospital stay, but the quality of evidence is low. Breath focus with deep belly breathing is a well-known relaxation technique that is easy to learn. It can disengage the mind from distracting thoughts and sensations. The respiratory system is closely connected to the autonomic nerve system (ANS) via the vagal nerve. When breathing is manipulated to a slow frequency, it can increase vagal activity, decrease anxiety and reduce mean blood pressure. Stimulation of the vagal nerve is also known to decrease hyperalgesia and mitigate release of pro-inflammatory cytokines. The maximum effect is typically observed at a respiratory frequency around 6 breaths per min (0.1 Hz). This breathing technique is endorsed by the National Health Service (NHS) of the United Kingdom (U.K.) to reduce stress and anxiety. The application of slow-paced breathing and its vagus-mediated effect on has not yet been investigated in the clinical perioperative setting.

### 1.3 Aim

Slow-paced breathing in this trial is deep belly breathing around a frequency of 6 breaths per min and called Slow PACE breathing in this study. Participants will be trained in Slow PACE breathing pre-operatively and will practice the relaxation technique daily. We aim to examine the effects of Slow PACE breathing in breast cancer patients undergoing surgery on perioperative anxiety, performed at induction of anesthesia.

Performance at induction of anesthesia is chosen as defined intervention to be able to closely monitor non-compliance. If a participant does not manage to perform Slow PACE breathing after training at induction, she will be considered non-compliant.

We further aim to explore effects on blood pressure, per-operative need of hypnotics, postoperative pain and opioid use, PONV and patient satisfaction.

## 2. OBJECTIVES

Primary Objective: The present study aims to examine the effects of pre-trained Slow PACE breathing performed at induction of anesthesia in patients undergoing surgery for breast cancer on anxiety, scored by Spielberger's State-Trait Anxiety Inventory, state scale (STAI-S), compared to usual care.

Secondary Objectives: To examine the effect of pre-operative Slow PACE breathing compared to usual care on:

- mean blood pressure before induction
- need of hypnotics during induction
- post-operative pain and need of opioids
- postoperative nausea and vomiting (PONV)
- patient satisfaction
- compare anxiety trait scored by Spielberger's State Anxiety Inventory (STAI-T) and general anxiety scored by the anxiety subscale of the Hospital Anxiety and Depression Scale (HADS-A) at baseline

### 2.1 HYPOTHESIS

Pre-trained Slow PACE breathing performed at induction of anesthesia attenuates perioperative anxiety.

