### 4.4 Sample size calculation

With 75 patients per arm, 96% power would be achieved to detect a difference of 5 points in STAI-S score between intervention and control, with a mixed model analysis of repeated measures, at the two-sided 5% significance level in a design with 3 measurements per patient (baseline before surgery, at pre-operative holding and on day 1 post-operatively) having an autoregressive order 1 covariance structure when the standard deviation is 10 and the correlation between observations within the same patient is 0.6. The PASS software module for the test of two means in a repeated measures design was used for this calculation. Accounting for 5% drop-outs/non-compliant patients, 79 patients per arm (total 158) would be needed.

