## 5. TREATMENT OF SUBJECTS

### 5.1 Investigational treatment

#### Intervention group:

The intervention consists of performance of pre-trained Slow PACE breathing by the patient at induction of anesthesia for breast cancer surgery.

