##### *Baseline and surgery parameters*

- Age
- Length and weight
- American Society of Anesthesiologists classification (ASA class)
- Sociodemographic status (household, marital state, employment, education)
- Intoxications
- History of sedative or anti-depressive medication use
- Type of breast cancer and type of breast cancer surgery
- Underlying disease(s)

*Intraoperative*

- The following vital signs are scored at baseline (e.g. measured on the outpatient department), at arrival on the operation room, just before induction and at the first measurement after induction:
  - Systolic-, diastolic-, and mean blood pressure (mmHg)
  - Heart rate (beats per minute)
  - Oxygen saturation (SpO2 in %)
  - Respiratory rate (breaths per minute)
- Type and dose of anesthetic medication used for induction of anesthesia
- Type and dose of vasoactive medication used during or within five minutes after induction
- Anesthetic medication used for maintenance of anesthesia
- Type and dose of administered opioids
- Type and dose of other analgesia
- Anti-emetics used
- Perioperative anesthesiological management regarding locoregional techniques
- Duration of anesthesia
- Duration of surgery

*Postoperative - recovery room*

- Vital signs
- Highest NRS during admission in the recovery room
- Mean cumulative intravenous opioid dose administered during admission in the recovery room (MEQ)
- Postoperative nausea or vomiting (Y/N)

**8.2 Randomisation, blinding and treatment allocation***Randomisation*

Patients will be randomly allocated to the study arms (usual care or Slow PACE breathing) using blocked randomization with age (<50 versus ≥50) as randomisation stratification factor in Castor.

*Blinding*

In this trial it is not possible to blind the patient or the investigators.

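### The hypothesis credits breathing performed at induction, but the primary STAI-S analysis can support a conclusion only about the assigned Slow PACE programme, and 10.3 does not name its contrast

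*Combined protocol and SAP*

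**What the plan says.** **Treatment under test.** Section 2.1 states: "Pre-trained Slow PACE breathing performed at induction of anesthesia attenuates perioperative anxiety". The primary objective in section 2 is to examine the "effects of pre-trained Slow PACE breathing performed at induction of anesthesia in patients undergoing surgery for breast cancer on anxiety". Section 5.1 says: "The intervention consists of performance of pre-trained Slow PACE breathing by the patient at induction of anesthesia for breast cancer surgery". Section 1.3 gives the reason for naming this moment: "Performance at induction of anesthesia is chosen as defined intervention to be able to closely monitor non-compliance".

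**Training.** Sections 5.1 and 8.3.3 give the intervention arm a video, a video-call and daily practice after the baseline questionnaires. Under 11.6, controls can have the material on request once the study is over.

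**Measurements.** Section 4.4 lists three: "baseline before surgery, at pre-operative holding and on day 1 post-operatively". Section 8.3.2 likewise places T1 shortly before surgery on the day itself. Under 8.3.3 the guided breathing begins in the operating room, after the time-out.

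**Analysis.** Section 10.2 makes the analysis intention-to-treat. Section 10.3 fits a mixed model to T1 and T2, adjusted for baseline STAI-S and age group, with the correlation structure chosen by corrected AIC and BIC. It lists arm comparisons of the T0-T1, T1-T2 and T0-T2 changes as additional analyses. It does not say whether the primary test is an average, a single time point, a joint test or an interaction.

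**The concern.** The wording ties the effect to what the patient does at induction. One of the two scores in the primary model is taken before that happens, and both come after weeks or days in which only one arm was trained. A positive primary result would naturally be reported as support for 2.1, and so could credit breathing at induction with a difference that was already present in holding.

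The unnamed contrast adds to this. If 10.3 is read as one common arm effect, the balance between the score before induction and the score after surgery is not fixed in advance. It depends on which covariance structure the information criteria select.

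**Working it through.** **Order of events**

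| Event | Intervention | Control | Section |
|---|---|---|---|
| T0 questionnaires | yes | yes | 8.3.2 |
| Video, call, daily practice | yes | no | 5.1, 8.3.3, 11.6 |
| T1, pre-operative holding | yes | yes | 4.4, 8.3.2 |
| Guided breathing after time-out | yes | no | 8.3.3 |
| T2, day 1 | yes | yes | 4.4, 8.3.2 |

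Every comparison that uses T1 or T2 sets trained patients against untrained ones. T1-T2 spans the breathing at induction, but also surgery and any lasting effect of training.

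**Inputs (4.4).** SD 10, AR(1) correlation 0.6, 75 per arm, two-sided 5%, difference 5 points. With v the variance of the contrast for one patient, SE = √(2v/75) and power ≈ Φ(δ/SE − 1.96).

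**The plan's own figure.** For the mean of T0, T1 and T2:
- v = (100/9) × [3 + 2(0.6 + 0.6 + 0.36)] = 68.0
- SE = 1.347
- power = Φ(3.713 − 1.96) = 0.960

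The stated 96% reproduces, and 75/0.95 = 78.9 gives 79 per arm. The figure is an average that includes baseline. Section 10.3 instead uses baseline as a covariate, so 4.4 does not settle which contrast 10.3 tests.

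**Covariance of T1 and T2 given T0**
- Var(T1) = 100 − 60²/100 = 64
- Var(T2) = 100 − 36²/100 = 87.04
- Cov = 60 − 60 × 36/100 = 38.4

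**Weights for one common arm effect.** Generalised least squares gives T1 the weight (87.04 − 38.4)/(64 + 87.04 − 2 × 38.4) = 48.64/74.24 = 0.655, and T2 the weight 25.6/74.24 = 0.345. The variance is (64 × 87.04 − 38.4²)/74.24 = 55.17, SE 1.213. If the chosen structure forces equal variances, the weights are 0.5 and 0.5.

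**Fixed equal-weight average.** v = (64 + 87.04 + 76.8)/4 = 56.96, SE 1.232.

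**Single times.** SE is √(2 × 64/75) = 1.306 at T1 and √(2 × 87.04/75) = 1.524 at T2.

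**Power.** The patterns (5,0) and (0,5) are assumptions, not protocol figures.

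| Effect at T1, T2 | Common effect, 0.655/0.345 | Equal-weight average | T1 alone | T2 alone |
|---|---|---|---|---|
| 5, 5 | 98.5% | 98.2% | 96.9% | 90.7% |
| 5, 0 | 77% | 53% | 96.9% | 5% |
| 0, 5 | 30% | 53% | 5% | 90.7% |

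For example, (5,0) under the common effect estimates 0.655 × 5 = 3.28 points, and Φ(3.28/1.213 − 1.96) ≈ 0.77.

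**Precision.** 95% half-widths (1.96 × SE) are 2.6 points at T1, 3.0 at T2 and 2.4 for the equal-weight average. For the T1-T2 change given T0, v = 74.24, SE = 1.407 and the half-width is 2.8.

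**The case against.** The strongest reply is that the programme is already the intervention. The breathing is described as pre-trained, 5.1 has its own part on training, and the Summary and 1.3 both describe daily practice. Section 1.3 explains that induction was named so that compliance could be observed. The outcome in 2.1 is perioperative anxiety, not anxiety after induction, and the arms are compared as randomised. The change comparisons in 10.3 already show when a difference arises.

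Much of this stands. The assigned arm includes training, and no passage claims to separate performance at induction from it. A reader might infer that the primary comparison is confounded or that the sample size is wrong. The documents support neither: the randomised comparison of the assigned strategies is valid, and the 96% reproduces.

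What remains is narrower. Calling the breathing pre-trained makes training a condition for the performance, which is still the named cause. No passage limits the conclusion to the whole programme. The change comparisons are additional, and nothing ties them to how the primary result is read.

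It is also fair to say that fixing an equal-weight average does not stop a significant result from coming wholly from T1, since (5,0) still has 53% power. That risk is met by the wording of the conclusion and by showing the time-specific estimates. The named contrast only stops the weighting from depending on the data.

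**Conclusion.** The point holds as one of interpretation and specification, minor to should-fix. The trial can conclude that assignment to the Slow PACE programme changes perioperative state anxiety relative to usual care. It cannot conclude that breathing at induction does so, and part or all of a significant primary result could come from T1.

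The size depends on a reading that 10.3 leaves open. If 5 points were gained at T1 and none at T2, the primary test would be significant with probability of about 77% as a common effect with weights 0.66/0.34, or 53% with equal weights. If the gain came only at T2, the figures would be about 30% and 53%. With 5 points at both times the choice hardly matters (98.5% and 98.2%). These values rest on the SD, correlation and 75 per arm in 4.4, on a normal approximation and, for the one-time patterns, on assumed effects. The 0.66/0.34 weights also assume a fitted structure that lets the variances differ.

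**What to change.** 1. In 2, 2.1 and 10.3, state the conclusion as the effect of assignment to the Slow PACE programme (training, daily practice and guided performance at induction) against usual care. Add that T1 precedes performance at induction and that no planned comparison separates that performance from training and practice. Leave the compliance definition and the per-protocol set unchanged, and describe the per-protocol result as relating to performance at induction only.
2. In 10.3, include arm-by-time and pre-specify one primary contrast with fixed weights. The equal-weight average of the baseline-adjusted T1 and T2 differences is one option. Present it as a choice, since the calculation in 4.4 averages over T0 as well.
3. Report the T1 and T2 differences and the already planned T0-T1, T1-T2 and T0-T2 comparisons with 95% confidence intervals beside the primary result.

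The cost is some wording, one interaction term and one named contrast, with no new data or patients. The claim becomes narrower, and the single-time estimates, which are supportive, are slightly less precise than the average.

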### **3. STUDY DESIGN**

Single center, two-group, prospective, randomized controlled trial of patients scheduled for surgery for breast cancer. The trial will be conducted according to Good Clinical Practice (GCP) Guidelines and comply with the principles of the Declaration of Helsinki, all applicable national (WMO) and general data protection regulations (GDPR).

## 4. STUDY POPULATION

### 4.1 Population (base)

We aim to include patients undergoing surgery for breast cancer in the Antoni van Leeuwenhoekziekenhuis.

### 4.2 Inclusion criteria

In order to be eligible to participate in this study a subject must meet the following criteria:

- Female
- Undergoing surgery for breast cancer in the Antoni van Leeuwenhoekziekenhuis

### 4.3 Exclusion criteria

A potential subject who meets any of the following criteria will be excluded from participation in this study:

- Age < 18 years
- ASA  $\geq$  4
- History of severe pulmonary illness: severe asthma or severe chronic obstructive pulmonary disease (COPD) GOLD III or IV
- Unable to give written or oral informed consent
- Patient refusal
- Not able to understand Dutch
- No internet access
- Visual or hearing impairments interfering with reading and listening to the online material

### 4.4 Sample size calculation

With 75 patients per arm, 96% power would be achieved to detect a difference of 5 points in STAI-S score between intervention and control, with a mixed model analysis of repeated measures, at the two-sided 5% significance level in a design with 3 measurements per patient (baseline before surgery, at pre-operative holding and on day 1 post-operatively) having an autoregressive order 1 covariance structure when the standard deviation is 10 and the correlation between observations within the same patient is 0.6. The PASS software module for the test of two means in a repeated measures design was used for this calculation. Accounting for 5% drop-outs/non-compliant patients, 79 patients per arm (total 158) would be needed.

**Feasibility analysis**

After inclusion of 30 patients, we plan to assess the compliance to Slow PACE breathing just before induction. A failure to compliance is when a patient in the intervention group does not perform the guided Slow PACE breathing at induction of anesthesia, defined as breathing at rate of  $\geq 10$  breaths per minute. Assuming 95% patients will comply, the lower limit of a binomial exact 95% confidence interval for the compliance rate will be 80%. If the lower limit of the 95% confidence interval for the compliance rate is below 80%, then additional strategies will be deployed to ensure patients adhere to the training of the breathing technique (e.g. weekly calls to check-up and remind the patients) and patients with failure to compliance will be reviewed for point of improvement to increase compliance.

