### 8.3.4 Other study procedures

#### *Preoperative*

To monitor participation to the daily training sessions, participants in the intervention group will receive a daily email with a reminder and a link to the electronic CRF (Castor), in which they can score if they had time to practice the slow-paced breathing the day before (Y/N).

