### 10.2 Analysis sets

Analyses will be performed on an intention-to-treat (ITT) basis on all randomized patients. A per-protocol analysis set (PPS) will comprise all randomized patients excluding the non-compliant. Additional sensitivity analyses will be performed on the PPS.

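### The compliance check is timed at 30 included patients, but its stated 80% lower limit needs 30 intervention patients; with about 15 in that arm, even full compliance gives 78.2%

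*Combined protocol and SAP*

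**What the plan says.** The Feasibility analysis in section 4.4 has four elements.

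- **Timing:** "After inclusion of 30 patients, we plan to assess the compliance to Slow PACE breathing just before induction". No arm is named.
- **Who can fail:** "A failure to compliance is when a patient in the intervention group does not perform the guided Slow PACE breathing". A rate of 10 or more breaths per minute counts as failure.
- **Stated precision:** "Assuming 95% patients will comply, the lower limit of a binomial exact 95% confidence interval for the compliance rate will be 80" percent.
- **Action rule:** "If the lower limit of the 95% confidence interval for the compliance rate is below 80%, then additional strategies will be deployed". Weekly calls are given as an example, and patients who failed are reviewed.

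The sample size paragraph of section 4.4 plans equal arms: "79 patients per arm (total 158) would be needed". Section 8.2 specifies blocked randomisation stratified by age, without a block size. No other section restates how many patients the check will assess.

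**The concern.** The number that times the check and the number that enters the compliance rate are not the same. Controls are not asked to do the breathing, so they cannot contribute to the rate. With equal arms, about half of the first 30 included patients are assessable, yet the stated lower limit looks like a calculation on 30.

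The threshold makes this matter. The exact lower limit depends strongly on sample size, and at about 15 patients it may be unable to reach 80% at all. The decision would then be fixed before any data are seen, and extra contact would go automatically to one arm of an unblinded trial. This is the only planned early look at an assumption that the design uses elsewhere: section 4.4 allows 5% for drop-out and non-compliance together, and section 10.2 defines the per-protocol set by compliance.

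**Working it through.** **Inputs.** From section 4.4: assumed compliance 95%, exact binomial 95% interval (taken as two-sided Clopper-Pearson), threshold 80%, check at 30 included, 79 per arm. The 1:1 allocation is inferred from the equal arms, giving 30 / 2 = 15 intervention patients.

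**Formula.** For x compliant patients out of n, the lower limit is the 2.5% quantile of a Beta(x, n − x + 1) distribution. When x = n, this reduces to 0.025^(1/n).

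**Step 1: reproduce the plan's figure.** With n = 30 and x = 0.95 × 30 = 28.5, the lower limit is 80.3%. This matches the stated 80%.

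**Step 2: the same calculation at n = 15.** With x = 0.95 × 15 = 14.25, the lower limit is 70.4%. Other methods at the same n and rate give 74.3% (one-sided exact), 72.4% (Wilson), 75.4% (Jeffreys) and 70.1% (Agresti-Coull). None gives 80%.

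**Step 3: attainable results.** Neither 28.5 nor 14.25 can be observed. The limits for whole counts are:

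| Compliant / assessed | Lower limit | Below 80%? |
|---|---|---|
| 14/15 | 68.1% | yes |
| 15/15 | 0.025^(1/15) = 78.2% | yes |
| 16/16 | 0.025^(1/16) = 79.4% | yes |
| 17/17 | 0.025^(1/17) = 80.5% | no |
| 28/30 | 77.9% | yes |
| 29/30 | 82.8% | no |

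With 16 or fewer assessed patients, no result avoids the trigger. Passing needs at least 17 assessed patients, all compliant, or at least 26 if one fails (25/26 gives 80.4%).

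**Step 4: how the rule behaves with 30 intervention patients.** The trigger is two or more failures. With true compliance p, its probability is 1 − p^30 − 30(1 − p)p^29:

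- p = 0.95: 1 − 0.215 − 0.339 = 0.446, or 45%
- p = 0.90: 82%
- p = 0.80: 99%

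**Step 5: count rules at n = 15, for comparison.**

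| Trigger | p = 0.95 | p = 0.90 | p = 0.80 |
|---|---|---|---|
| 2 or more failures of 15 | 17% | 45% | 83% |
| 3 or more failures of 15 | 4% | 18% | 60% |

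**Step 6: timing.** Thirty included patients are 30/158 = 19% of the trial. Thirty intervention patients need about 60 randomised, or 60/158 = 38%.

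**The case against.** The strongest reply is that nothing was miscalculated. The 80% is right for 30 assessed patients, the same paragraph defines failure in the intervention group, and so 30 intervention patients were probably meant. On that view only a qualifier is missing. This may well be the intention, but the text does not say so. A team following it literally would run the check at 30 included, with a rule that cannot be passed.

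A second reply is that the split at 30 is not certain to be 15:15. The block size is not given and blocks are formed within two age strata, so 17 or more intervention patients are possible. That stands, but it helps little: all 17 would have to comply, which at 95% compliance has probability 0.95^17 = 42%.

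It could also be fewer than 15. Section 11.2.1 puts first contact at least two weeks before surgery, and compliance is seen only at induction. However, that interval refers to the first phone call, and the text does not rule out waiting until the included patients reach surgery. So a smaller number is possible but not established.

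Third, a cautious trigger for a low-burden response need not have a low false-alarm rate, and an automatic trigger would still leave an estimated rate and a review of any failures. Both points are fair. Publishing trigger probabilities is good practice, not a correction of an error. What the rule loses is its ability to separate good from poor compliance.

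Finally, the stakes are modest. The check is not a stopping rule and does not change the sample size. The intervention arm already has a kick-off video-call, and "participants in the intervention group will receive a daily email with a reminder". The primary analysis is unchanged: "Analyses will be performed on an intention-to-treat (ITT) basis on all randomized patients". This limits the severity but does not remove the inconsistency.

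**Conclusion.** The concern holds. The timing, the stated limit and the threshold in the Feasibility analysis cannot all be right together.

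- **As worded (about 15 assessed):** the lower limit at 95% compliance is about 70%, not 80%. The trigger is certain with 16 or fewer assessed patients.
- **If 30 intervention patients were meant:** the 80% is a fair planning approximation, although the attainable limits on either side are 77.9% and 82.8%. The check works but is conservative, firing 45% of the time at the compliance it assumes.

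This rests on 1:1 allocation, inferred from equal arm sizes, and on a two-sided Clopper-Pearson interval, which is the reading that reproduces the plan's figure. A one-sided exact limit would be 81.9% at 15/15, so the check could then be passed, but it gives 74.3% at 95% compliance and does not rescue the stated 80%. The point should be fixed, but it does not threaten the primary analysis.

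**What to change.** Define the denominator in section 4.4 as intervention-group patients who have reached induction, and make the timing, limit and trigger agree. There are two ways.

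- **Option A: assess 30 such patients.** Replace the single 80% figure with the attainable limits (82.8% at 29/30, 77.9% at 28/30). State that two or more failures trigger action, with probability 45%, 82% and 99% at true compliance of 95%, 90% and 80%. The cost is a later check, at about 60 randomised instead of 30 included.
- **Option B: keep the check at about 15 such patients.** Correct the stated limit to about 70% (78.2% at 15/15, 68.1% at 14/15) and replace the 80% lower-limit trigger with one that can be met at that size. A count rule from Step 5 is one possible form. The cost is sensitivity: at 90% compliance, two or more failures of 15 triggers 45% of the time, against 82% for the 30-patient rule.

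Either option changes about two sentences and leaves the sample size and the primary analysis as they are.
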